To assess bone quality and its effect on glenoid component loosening, we will take humeral head bone samples from all patients. These bone samples will be assessed by microCT to measure trabecular bone volume and connectivity as well as by mechanical testing. These data will be correlated with the trabecular bone volume of the glenoid defined by the pre-operative CT scans. In addition all bone quality measurements will be correlated with CT scan imaging of the glenoid at the time of surgery and at two year follow up.

In order to acquire consistent information on bone quality across the patients, a custom-made calibration phantom object will be located between the CT bed and the patient. The phantom object consists of three cylindrical rods, each with a known density of hydroxyapatite (0, 500, and 1,000 mgHA/cm³) embedded in a soft foam block. The grey-level of pixel from the rods will be used to calibrate the Hounsfield units and the corresponding bone density using custom-written software.

Patient Enrollment

The proposed clinical trial will randomly enroll patients indicated for standard of care anatomic total shoulder arthroplasty into one of the four treatment groups. Our goal is to have 20 subjects in each treatment group. To accomplish this goal, we will enroll up to 120 subjects to control for subject withdrawal after enrollment. To enroll at least 20 patients into each group, including Group 5 (SmartBase), new randomization envelopes will be generated that start at number 34. The distribution of patients into Groups 1 – 4 at the time that Group 5 was begun is:

Group 1: 8
Group 2: 7
Group 3: 7
Group 4: 10

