Post-operatively, all patients will receive a CT with MAR and RSA (if chosen) within 3 weeks of surgery. This will be a CT Scan performed with the patients arm by the side in a supine position using metal artifact reduction techniques. In addition patients will receive a second CT scan RSA imaging, provided they originally got RSA, performed 2 to 3 years (\pm 2 months) after surgery. The second CT scan will be performed with MAR techniques and with the patient in the arm by the side position again using metal artifact reduction techniques. We have shown that in a small number of patients the glenoid component can shift in position within the first 3-6 months after surgery making the first CT Scan more accurate for implant position. The images obtained from the post-operative CT scans are placed back into the surgical software and the 3D reconstruction of the post-operative

scapula with the implants is compared to the pre-operative plan. Using measurement tools within the software, developed at Cleveland Clinic, we will compare the position of the actual glenoid component placed in the patient with the desired position specified by the pre-operative plan. The use and validation of these imaging methods to precisely measure implant position has been performed at the Cleveland Clinic in a prior IRB approved studies (IRBs 10-582, 12-997 and 13-652).

Pre-operatively, the high resolution quantitative CT will measure volumetric bone mineral density and the trabecular network of the glenoid. When available, this will be applied to the pre-operative CT for those patients at Main Campus. Patients who have their pre-operative CT completed at non-Main Campus facilities will have the standard of care pre-operative CT. This will be done at the same visit for the standard of care pre-operative CT. Micro CT imaging, which creates a 3D reconstruction of the fine bone structure, in addition to microarchitecture analysis and mechanical testing, will allow assessment of the bone tissue taken from the bone core sample. Between the preoperative imaging and the bone tissue analysis, we will have data to properly determine the quality of the bone stock surrounding the implant. Further correlating this with RSA and 3D CT imaging of implant movement, we can fully develop the cause and effect of bone quality on glenoid component loosening.

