The IRI legs are placed virtually (manually) on a virtual SmartBone using an impact detection function in the 3D modeling software. From there the height of each IRI leg is measured and correlated to a number on the SmartBase. The SmartBase has hashes in 1/2 mm increments. The surgeon is then given a pre-operative plan that includes virtual photos of the IRI placement, the IRI leg lengths and numbers of each SmartBase height as calculated. Intra-operatively the IRI is assembled as normal and placed onto the SmartBase after each adjustable tab has been set to the appropriate height for each leg. The IRI is then used as normal.

Inclusion/Exclusion Criteria:

To be eligible for inclusion, a primary anatomic total shoulder arthroplasty must be indicated for the patient.

Outcome Measures:

By comparing computer generated pre-operative plan to post-operative component placement, we will be looking at three outcomes. First, we will compare the overall difference in component placement between the four treatment groups: SOC instrumentation, SOC instrumentation with SmartBone, intelligent reusable instrument with metal instead of plastic legs, and real time instrumentation. Secondly, we will compare the placement between the technologies within and between surgeons. All of the surgeons have extensive experience with anatomic total shoulder arthroplasty. Two of the surgeons have extensive experience with the pre-operative planning and the IRI and RTI technology. Thirdly, we will evaluate the difference in implant position between technologies based on severity of pathology. The quality of the bone core samples will be correlated to the possible loosening of the implants.

Sample Size:

We intend to have approximately 20 subjects in each of the 4 treatment groups. We expect to randomize up to 120 subjects to achieve 20-25 subjects in each treatment group.

Data Analysis

Average deviations from plan for the four treatment groups will be compared using mixed-effects ANOVA methods. Random effects will be included to account for correlation between observations introduced as a consequence of multiple observations of deviation being taken on a particular surgeon. If significant differences are found, multiple comparisons based on the ANOVA model will be made to compare each pair of groups, and will use Holm's step-down procedure to control the family-wise error rate of the tests.

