All analyses will be done using R software (version 3.0.0, Vienna, Austria). A significance level of 5% will be used for all testing.

Data Sheets

Clinical data collected pre- and post-operatively will be passive and active range of motion, manual muscle strength testing and shoulder functional scores, and co-morbidities, all of which are standard of care. Post-operative data will be collected at two years (\pm 2 months) after surgery. We will collect at the time of surgery the implant used, the time for surgical care glenoid exposure to end of pin placement. The implant used, the surgical instruments used and any comments from the surgeon as to the ease of use and accuracy of the instruments. Verbatim comments will be solicited and recorded by a research assistant attending all surgical procedures.

Pre-operative imaging data will include: glenoid version and inclination, estimated pre -morbid inclination, version and depth of glenoid bone loss using the glenoid vault model, preferred implant type inclination and version.

Post-operative implant placement to desired location will be defined for the location of the center peg of the implant in the superior/inferior (SI), anterior/posterior (AP) and medial/lateral (ML) dimension in millimeters and the trajectory of the center peg vs plan in version and inclination. The location of the implant in relation to the joint line as measured by the glenoid vault model will be measured in millimeters. Back side contact of the implant to the bone will be measured as a surface area in direct contact with the bone and any lucent lines around the implant pegs will be measured. Peg perforation and the location of the peg perforation will be recorded. The tantalum beads within each implant will be measured for translational or rotational movement.

Changes in implant position from post-operative CT scan (CT 1) vs the first post-operative CT scan (CT 2) will be correlated with back side seating, implant type, medialization of the joint line and peg perforation and severity of the post-operative pathology.

Study data will be collected and managed using REDCap (Research Electronic Data Capture). Tracking data will be stored in an Excel spreadsheet, which will exist only on password-protected computers or on restricted-access CCF servers. Only study personnel will have access to the data.

Adverse Events and Data Monitoring Committee (DMC):

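### The bone-quality aim is worded as cause and effect, but bone quality is only observed and only correlation is planned, so the design can support an association at most

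*Combined protocol and SAP*

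**What the plan says.** The causal claim is one sentence in Detailed Study Design: after correlation with RSA and 3D CT movement, "we can fully develop the cause and effect of bone quality on glenoid component loosening". Two other sections describe the same analysis in weaker terms. Bone Quality Measurements says that "all bone quality measurements will be correlated with CT scan imaging of the glenoid at the time of surgery and at two year follow up". Outcome Measures says: "The quality of the bone core samples will be correlated to the possible loosening of the implants". Loosening is not defined in either place.

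Bone quality is measured, not assigned: "we will take humeral head bone samples from all patients". What is assigned is instrumentation. Patient Enrollment says the trial will "randomly enroll patients indicated for standard of care anatomic total shoulder arthroplasty into one of the four treatment groups", with a fifth group added later.

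Data Analysis specifies one model, a mixed-effects ANOVA of deviation from plan by group with random effects for surgeon. It does not cover bone quality or loosening. Data Sheets adds that change in implant position between the post-operative scans "will be correlated with back side seating, implant type, medialization of the joint line and peg perforation and severity of the post-operative pathology". It does not say whether any of these factors enters the bone-quality analysis.

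**The concern.** Randomisation protects the comparison of instruments. It gives no protection to a comparison of patients with better and worse bone, who may differ in other ways that affect implant movement. The plan itself expects movement to be related to pathology severity and implant type. Detailed Study Design also has the surgeon choose the implant after assessing the glenoid pathology. If pathology is related to bone quality as well, a crude correlation mixes its effect with that of bone quality.

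At stake is the conclusion of this aim. A correlation might be reported as showing that poor bone causes loosening when the data cannot separate that explanation from others. Because no model is named in advance, the choice of adjustment would also be left until the data are seen.

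**Working it through.** The plan gives no effect size, power or standard deviation for this aim, so there is no stated figure to reproduce. The defect follows from the text: the exposure is observed, the method is correlation, and the conclusion is causal. The arithmetic only shows how large the problem could be.

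**Inputs from the documents**
- Significance level 5% (Data Analysis). Sidedness is not stated; two-sided is assumed.
- n = 4 × 20 = 80 (Sample Size), n = 5 × 20 = 100 with Group 5 (Patient Enrollment), and n = 20 for the RSA subset at its maximum (Measurement of Implant Position).

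**Assumptions**
- One confounder, correlated *a* with both bone quality and movement, with *a* from 0.3 to 0.6. The documents give no value.
- No effect of bone quality on movement.
- Complete data: every patient has a bone-quality measure and both post-operative scans.

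**Formulas**
- Correlation produced by the confounder alone: r = a × a.
- Probability of a significant crude test (Fisher z): m = atanh(r) × √(n − 3); P = Φ(m − 1.96) + Φ(−m − 1.96).

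**Two cases at n = 80**, where √77 = 8.775
- a = 0.3: r = 0.09, atanh(r) = 0.0902, m = 0.792; P = Φ(−1.168) + Φ(−2.752) = 0.121 + 0.003 = 0.124.
- a = 0.6: r = 0.36, atanh(r) = 0.3769, m = 3.307; P = Φ(1.347) + a negligible term = 0.911.

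| a | r | n = 20 | n = 80 | n = 100 |
|---|---|---|---|---|
| 0.3 | 0.09 | 7% | 12% | 14% |
| 0.4 | 0.16 | 10% | 29% | 36% |
| 0.5 | 0.25 | 18% | 61% | 71% |
| 0.6 | 0.36 | 34% | 91% | 96% |

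Simulation (4,000 runs per setting, a = 0.3, 0.5 and 0.6) agreed to within about one percentage point. Testing the partial correlation given the confounder brought the rate back to about 4% to 5% in every setting. That result requires the confounder to be well measured and to be the only one.

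**Scale.** The smallest correlation detectable with 80% power is tanh(2.80/√(n − 3)): 0.31 at n = 80, 0.28 at n = 100 and 0.59 at n = 20. With *a* of 0.5 to 0.6, the confounded correlation (0.25 to 0.36) is about as large as the smallest true one the trial could reliably find at n = 80 or 100.

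**Cost of adjustment.** Intercept 1, bone quality 1, version, inclination and depth of bone loss 3, three surgeons 2: seven parameters against two. Residual degrees of freedom fall from 78 to 73 at n = 80, from 98 to 93 at n = 100, and from 18 to 13 at n = 20.

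**The case against.** The strongest reply is that this is one sentence of design narrative. Bone quality is not among the three numbered outcomes, two of the three sections on this analysis already use the language of correlation, and the randomised comparison is untouched. That is true, and it makes the point a low priority. It does not make the sentence correct.

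Four stronger readings are tempting, and the documents do not support them.

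- A reader might infer that the plan prescribes unadjusted analysis, with each factor correlated separately. It says neither. It names correlation and is silent on adjustment, and Data Sheets lists the factors in one sentence without saying whether they are analysed singly or jointly.
- A reader might infer that pathology is a known confounder. The documents connect pathology with implant choice, and both with movement as something to be examined. Nothing connects pathology or implant type with bone quality, so that link is a possibility only.
- A reader might rest the case on one assumed value. With a = 0.45, r = 0.2025, which is p = 0.04 at n = 100 but p = 0.07 at n = 80 and p = 0.39 at n = 20. Only a range is informative.
- A reader might want every factor listed in Data Sheets adjusted for. Seating, medialization and peg perforation arise at or after surgery and may lie on the path from bone quality to movement, so adjusting for them could remove part of the effect sought. Implant type may raise the same problem, because it is chosen after the glenoid is assessed.

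It can also be said that adjustment will not make the analysis causal. That stands too: unmeasured confounding would remain. This is why the wording has to change along with the model.

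**Conclusion.** The point holds in limited form. The plan draws a causal conclusion about a factor that it only observes, by a method that it describes only as correlation and with no adjustment specified. An exploratory association is the most this design can deliver.

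That conclusion needs no numerical assumption. The size of any false-positive problem does. The 12% to 91% (n = 80) and 14% to 96% (n = 100) figures show what assumed confounding of 0.3 to 0.6 on both sides would do; they are not estimates for this trial. Missing scans or bone measurements would reduce n and move the figures towards the n = 20 column.

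**What to change.** 1. In Detailed Study Design, replace the causal claim with an exploratory association between bone quality and implant movement, in line with Bone Quality Measurements and Outcome Measures.
2. In Data Analysis, replace the simple correlation with a regression of the change in implant position, from the early post-operative CT to the two-year CT, on bone quality. Adjust for surgeon and for the pre-operative glenoid measures listed in Data Sheets: version, inclination and depth of bone loss. Name in advance which bone-quality and position measures are used, since the plan records several of each.
3. Keep back side seating, medialization and peg perforation out of the main model, and state that this is because they may be mediators. Add implant type only as a sensitivity analysis. Assigned group is randomised and is not expected to confound bone quality.
4. Report the RSA subset descriptively; 20 patients leave 13 residual degrees of freedom for this model.

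The cost is a revised sentence, a short addition to Data Analysis, a weaker stated claim and five degrees of freedom. No new patients, visits or imaging are needed.

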Thus, to reach 20 in each group, randomization envelopes will be created by the statistician, [name] (QHS), that have 12, 13, 13, 10 and 20 in Groups 1-5, respectively. The change in the odds of being assigned to a particular group will change from 25% previously, to 15 to 19% in Groups 1-4, and to 29% in Group 5. They will receive all pre-operative testing, intra-operative care, including all implants and post-operative care that is standard of care and specific to the surgeon and patient decisions for care. The only change for this clinical trial will be the type of surgical instruments used to place the glenoid guide pin, retention of the humeral head for bone quality analysis, placement of the beads and post-operative CT scanning. In all cases the surgeon is able and allowed to use their own surgical judgment to place the guide pin, prepare the bone and place the desired implant. In all cases, the surgeon can use any and all of the standard instruments or guides provided by the implant manufacturer as the surgeon would use if the patient were not enrolled in the study. If the surgeon chooses not to use the IRI or RTI technique then this would be noted as a deviation in plan, the reasons would be recorded and the patient would be excluded from the study without post-operative imaging and their pre-

operative and intra-operative data would be analyzed for the purpose of understanding the reasons for failure of the RTI technology to provide assistance for refinement of the technology.

Detailed Study Design:

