The study will randomly enroll 20 patients into each of the four treatment groups. We will have three surgeons with experience in shoulder arthroplasty; two of these have extensive experience with the IRI, RTI and SmartBones technology. All patients will have the standard of care indications for an anatomic total shoulder arthroplasty and will give informed consent for both the surgery and participation in this study. Consent and enrollment will be obtained by the surgeon during a routine office evaluation. All patients will get standard of care pre-operative x-rays and CT scan at least one week prior to surgery. Scan quality must meet study specific criteria and we expect that the scans will be performed at Cleveland Clinic. The pre-operative CT scan will be placed within our pre-operative planning software (OrthoVis, Custom Orthopaedic Solutions, Cleveland, OH). The surgeon will use this software to assess the glenoid bone pathology and select the optimal implant and placement of that implant.

Patients will have standard of care indications for primary anatomic arthroplasty and be able to get a pre-operative shoulder CT scan at the Cleveland Clinic or at an outside facility so long as the study includes the entire scapula and has 1mm or thinner sections. These parameters are required for accurate pre-operative planning as well as comparison with the post-operative CT scans. Standard of care pre- and post-operative x-rays (AP and axillary views) will also be obtained and can be performed at Cleveland Clinic or acquired from another health care facility. In all patients the standard x-rays and CT images provided by the radiology department will be available to the surgeon before and during the surgery.

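### Group 5 (SmartBase) is randomised part-way through but has no specified analysis; adding it to the stated ANOVA without a stage term would put 0.35 to 0.50 of any between-stage drift into its contrasts

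*Combined protocol and SAP*

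**What the plan says.** Group 5 is described with the other groups under Glenoid Instrumentation and Pre-operative planning, where testing SmartBase in this trial is given as the purpose. Patient Enrollment says that "new randomization envelopes will be generated that start at number 34", lists 8, 7, 7 and 10 patients in Groups 1 to 4 when Group 5 began, and provides for envelopes "that have 12, 13, 13, 10 and 20 in Groups 1-5, respectively". It adds that the chance of assignment "will change from 25% previously, to 15 to 19% in Groups 1-4, and to 29% in Group 5".

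The rest of the plan still has four groups:

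- Patient Enrollment itself: patients are randomised "into one of the four treatment groups".
- Detailed Study Design: "The study will randomly enroll 20 patients into each of the four treatment groups".
- Outcome Measures: "we will compare the overall difference in component placement between the four treatment groups". The four are then named, and SmartBase is not among them.
- Sample Size: "We intend to have approximately 20 subjects in each of the 4 treatment groups".
- Data Analysis: "Average deviations from plan for the four treatment groups will be compared using mixed-effects ANOVA methods".

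Study Design, Methods also describes a four-group trial. The only model terms named are treatment group and random effects for surgeon. If the ANOVA is significant, all pairs are compared under Holm's procedure.

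**The concern.** There are two problems, and the first needs no assumption. Read literally, the plan randomises about 20 patients to Group 5 and leaves them out of its stated comparison. The second and third outcomes refer to technologies in general, with no comparator or model for SmartBase.

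The second problem arises if the analyst repairs this by changing four to five. Every Group 5 patient belongs to the second randomisation stage, while a third to a half of each other group belongs to the first. If deviation from plan changed between stages, for example through learning, patient mix or imaging, a model without a stage term would attribute part of that change to SmartBase. The direction is unknown. The bias could create a difference, or hide a real loss of accuracy relative to the IRI method from which SmartBase was derived.

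**Working it through.** **Inputs, all from Patient Enrollment.** First stage: 8, 7, 7, 10 and 0 in Groups 1 to 5, total 32. New envelopes: 12, 13, 13, 10 and 20, total 68.

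**The plan's own figures.** Shares of the new envelopes are 12/68 = 17.6%, 13/68 = 19.1%, 13/68 = 19.1%, 10/68 = 14.7% and 20/68 = 29.4%. These match the stated 15 to 19% and 29%. Each group totals 20, or 100 in all.

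**Bias with no stage term.** Let D be the shift in mean deviation from the first stage to the second, and f the first-stage share of a group. The expected difference, Group 5 minus Group k, is the true difference plus f × D, because Group 5 has f = 0.

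| Group 5 versus | f | Bias |
|---|---|---|
| Group 1 | 8/20 | 0.40 D |
| Group 2 | 7/20 | 0.35 D |
| Group 3 | 7/20 | 0.35 D |
| Group 4 | 10/20 | 0.50 D |

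Contrasts within Groups 1 to 4 carry only the difference in f: 0.05 (1 v 2, 1 v 3), 0.10 (1 v 4), 0.15 (2 v 4, 3 v 4) and 0 (2 v 3). A simulated mixed model with a random intercept for three surgeons and D = 1 gave 0.40, 0.33, 0.36 and 0.48 for the Group 5 contrasts (Monte Carlo SE about 0.02), and about 0 once a stage term was added.

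**Standard errors, in units of the residual SD.**

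- No stage term: √(1/20 + 1/20) = 0.316.
- With a stage term: √(0.1 + f²/W), where W = Σ 20 f(1 − f) = 20 × (0.24 + 0.2275 + 0.2275 + 0.25) = 18.9. This gives 0.329 (v 1), 0.326 (v 2 and v 3) and 0.336 (v 4), which is 3 to 6% larger.
- Within Groups 1 to 4, the worst case is √(0.1 + 0.15²/18.9) = 0.318, a loss of under 1%.
- Concurrent patients only: √(1/20 + 1/n) with n = 12, 13, 13 and 10 gives 0.365, 0.356, 0.356 and 0.387, which is 13 to 22% larger.

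**Error rates (D is an assumption).** The simulation used 100,000 runs, normal errors with SD 1, no true group effect, no surgeon effect and the same D in every group. An omnibus F test at 5% was followed by Holm on 10 pairs.

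| No stage term | D = 0 | D = 0.5 SD | D = 1 SD |
|---|---|---|---|
| Any false Group 5 difference | 1.6% | 3.8% | 10.0% |
| Family-wise error, all pairs | 3.5% | 5.4% | 10.8% |
| Coverage, unadjusted 95% CI, 5 v 1 | 95% | 91.3% | 81.4% |
| Coverage, 5 v 2 | 95% | 92.3% | 85.2% |
| Coverage, 5 v 3 | 95% | 92.4% | 85.4% |
| Coverage, 5 v 4 | 95% | 88.7% | 71.8% |

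With a stage term, the chance of any false Group 5 difference is 1.6% in all three cases and coverage stays at 95%.

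**The case against.** The strongest reply accepts that the four-group wording is out of date but disputes the weight of the drift argument.

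- **Drift is not shown.** The multiplier matters only if Group 5 is added, the stage term is left out, and drift exists. This is correct. At D = 0.5 SD the chance of a false Group 5 finding is 3.8%, still below 5%; clear inflation needs something like 1 SD. The estimates are nonetheless shifted at any D, whatever the tests do.
- **The range depends on final numbers.** If groups reach 25 with all extra patients in the second stage, the factors fall to 7/25 = 0.28 up to 10/25 = 0.40. Exclusions when the assigned instrument is not used would also move them. The new envelopes are, however, built to give exactly 20.
- **A stage term is not a complete remedy.** It assumes the same drift in every group. With a 1 SD drift in Groups 3 and 4 only, stage-adjusted coverage falls to about 90 to 92%. This stands, and it is why the concurrent-only analysis is needed alongside.
- **Surgeon effects may absorb some drift.** They do so only as far as drift comes from a changing surgeon mix, not from change over time within a surgeon.
- **The natural comparator is Group 3.** The plan presents SmartBase as derived from that group, and 5 v 3 has the lowest factor, 0.35. That is smaller, but not negligible.

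None of these points touches the missing analysis of Group 5.

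**Conclusion.** The concern holds and must be fixed. That Group 5 is randomised but has no specified analysis follows from the text alone. If it is added to the stated model unchanged, its contrasts carry 0.35 to 0.50 times any between-stage drift, assuming 20 analysed per group and the first-stage counts as listed (0.28 to 0.40 at 25 per group). The documents give neither the size nor the direction of drift, so the error rates and coverage figures illustrate what would follow and do not predict it. The problem is largely confined to Group 5: contrasts among Groups 1 to 4 carry at most 0.15 times the drift. A valid comparison is available from the patients randomised concurrently, but the plan does not specify it.

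**What to change.** 1. State five groups, naming SmartBase, in Study Design (Methods), Patient Enrollment, Detailed Study Design, Outcome Measures, Sample Size and Data Analysis.
2. Add to the mixed-effects ANOVA a fixed effect for randomisation stage (original envelope series versus new series).
3. Report stage-adjusted Group 5 contrasts with 95% confidence intervals, and a sensitivity analysis restricted to concurrently randomised patients (12, 13, 13, 10 and 20), which also guards against drift that differs by instrument.
4. Apply Holm to all 10 pairs.
5. Reconcile the 32 listed patients with new envelopes that start at 34, and say which stage number 33 belongs to. This may be no more than a withdrawal.

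The cost is wording plus one model term. Standard errors rise by 3 to 6% for Group 5 contrasts and by under 1% within Groups 1 to 4. Holm's first threshold becomes 0.05/10 = 0.0050 instead of 0.05/6 = 0.0083. These choices should be fixed before the data are analysed.

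### Prespecify adjustment for the pre-operative glenoid measures already collected, and name a severity analysis for outcome three; the gain in precision is modest and could be nil

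*Combined protocol and SAP*

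**What the plan says.** The Data Analysis section gives a single between-group model: "Average deviations from plan for the four treatment groups will be compared using mixed-effects ANOVA methods". The only other term it describes is for surgeon: "Random effects will be included to account for correlation between observations introduced as a consequence of multiple observations of deviation" within a surgeon. Pairwise tests with Holm's procedure follow if the overall test is significant. No patient-level covariate and no group-by-severity term is named.

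The Outcome Measures section lists three aims. The second is that "we will compare the placement between the technologies within and between surgeons". The third is that "we will evaluate the difference in implant position between technologies based on severity of pathology". It does not say which measure defines severity, or which model answers the third aim.

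The Data Sheets section shows that suitable measures will exist: "Pre-operative imaging data will include: glenoid version and inclination", with pre-morbid estimates, and "version and depth of glenoid bone loss using the glenoid vault model". The only analysis there that mentions severity correlates the change in implant position between the two CT scans with the severity of post-operative pathology. That compares neither technologies nor deviation from plan.

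Patient Enrollment describes no stratification by severity, and the eligibility statement sets no limit on glenoid deformity.

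**The concern.** Pre-operative glenoid anatomy is a natural candidate to predict how far an implant ends up from its plan. With about 20 patients per group, any deviation variance that it explains but that stays in the residual widens every group contrast. Without stratification, chance imbalance in severity also goes unadjusted. The difference in group means on a standardized measure has SD √(2/20) = 0.316, so two groups would differ by more than 0.5 SD about 11% of the time.

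The second matter is outcome three. Several candidate measures are collected and none is named, so the measure, any cut-point and the model could all be chosen after the data are seen. A severity main effect in the group model would not answer this outcome, which asks whether the difference between technologies depends on severity. That needs an interaction.

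**Working it through.** **1. The plan's own figures.** Sample Size gives about 20 per group with no effect size, SD or power, so that target cannot be re-derived. The envelope counts in Patient Enrollment do add up: 8+12, 7+13, 7+13, 10+10 and 0+20 each give 20.

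**2. Precision from three covariates.** Inputs from the documents are four analyzed groups of 20 (80 patients) and three surgeons (Detailed Study Design). R², the share of within-group deviation variance explained by the covariates, is assumed.

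- Residual df without covariates: 80 - 1 - 3 (groups) - 2 (surgeons) = 74.
- Average variance inflation from fitting three covariates: (74 - 1)/(74 - 3 - 1) = 73/70.
- Equivalent n per group = 20 × (70/73)/(1 - R²).
- Interval width ratio = √[(1 - R²) × 73/70].

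| Assumed R² | Equivalent n | Width ratio | Change |
|---|---|---|---|
| 0 | 19.2 | 1.021 | +2% |
| 0.10 | 21.3 | 0.969 | -3% |
| 0.20 | 24.0 | 0.913 | -9% |
| 0.30 | 27.4 | 0.854 | -15% |

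Break-even is R² = 1 - 70/73 = 0.041. A REML simulation with surgeon as a random effect (assumed surgeon SD 0.4, 2,500 trials per setting) agreed. Half-widths without and with the covariates were 0.632 and 0.645, 0.631 and 0.612, 0.634 and 0.579, and 0.632 and 0.541 SD. With five groups the equivalent n was 19.2, 21.2, 23.3 and 28.1.

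**3. What this means for a pairwise test.** At the strictest Holm step for six pairs (0.05/6 = 0.0083, two-sided assumed), the difference detectable with 80% power and no covariates is √(2/20) × (2.638 + 0.842) = 1.1004 SD by the normal approximation. Multiplying by the width ratios gives about 1.12, 1.07, 1.01 and 0.94 SD at R² of 0, 0.10, 0.20 and 0.30.

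**4. Outcome three as an interaction.** Take one continuous severity measure, standardized, with a slope in each of four groups of 20 and surgeon as a fixed effect.

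- The average of 1/SSx in a group is 1/(20 - 3) = 1/17.
- SE of a difference between two slopes is about √(2/17) = 0.343.
- Residual df = 80 - 4 - 4 - 2 = 70, so t = 1.994.
- Half-width = 1.994 × 0.343 = 0.68 SD of deviation per SD of severity.

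A simulation of 3,000 trials also gave 0.68, with power of 73% at a slope difference of 0.9 and 82% at 1.0.

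**5. Can exclusions after randomization make the omission a bias problem?** If an IRI or RTI guide is not used, "the patient would be excluded from the study without post-operative imaging"; the IRI and RTI technology sections have a matching rule for pins changed without the guide. No such rule is stated for Groups 1 and 2. The documents' only evidence on frequency is the background statement, just before Study Design, that the new instrumentation never had to be abandoned in 97 patients.

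- Exact two-sided 95% upper limit for 0 of 97: 1 - 0.025^(1/97) = 0.037.
- If the most severe 3.7% of a guide group were dropped, its mean severity would shift by φ(z)/(1 - f) = 0.0814/0.963 = 0.085 SD.
- The effect on mean deviation is √R² × 0.085 = 0.03 SD at R² 0.10 and 0.05 SD at R² 0.30, against a contrast half-width of about 0.63 SD.

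Adjustment removes such a shift only if exclusion depends on measured severity alone. As an illustration at an assumed 10%, if exclusion depended on the deviation itself the shift would be about 0.20 SD. After adjustment 0.18 SD (R² 0.10) or 0.14 SD (R² 0.30) would remain.

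**The case against.** The strongest reply is that covariate adjustment here is a preference. The planned ANOVA is valid without it, R² is unknown, and deviation is measured from a plan already tailored to each glenoid, which may remove much of the effect of anatomy. At R² of 0.10 the gain is only 3%, and below about 0.04 adjustment loses precision. All of this stands, and it limits the point to a modest improvement.

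A reader might infer that leaving out severity biases the group comparison. The documents do not support that. Omitting a baseline covariate does not bias a comparison that keeps all randomized patients. The exclusions are a separate problem that covariates do not repair. Exclusion rates of 10% or 20% have no source in the documents, and the reported 0 of 97 implies at most about 3.7%. That limit has its own weaknesses. The 97 include PSI patients, the metal legs and SmartBase are new, and abandoning an instrument may be a narrower event than changing a pin. The protocol also already plans to analyze excluded patients' pre-operative and intra-operative data to understand failures.

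A reader might also infer that the plan cannot examine how technology effects differ between surgeons, given that "Two of the surgeons have extensive experience with the pre-operative planning and the IRI and RTI technology". The text speaks of random effects in the plural without listing them, so a surgeon-by-group term is not ruled out. Detailed surgeon contrasts would be too imprecise to insist on, with half-widths of roughly 1.3 to 1.7 SD under assumed caseloads.

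**Conclusion.** The point holds as a modest improvement in precision, together with an outcome that needs a named analysis. The stated comparison is valid but does not use three pre-operative measures that the trial collects anyway. Adjustment would be worth between about one patient per group lost (R² of 0) and about seven gained (R² of 0.30). These figures assume four analyzed groups of 20, a roughly linear relation, and R² values that the documents do not give.

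Treating version, inclination and bone-loss depth as severity is a reasonable reading, not a definition in the documents. For outcome three the gap is mainly one of missing detail, and it can be closed by naming the measure and the interaction. Only a very large interaction, about 1.0 SD per SD of severity, could be detected with reasonable power. The material does not support calling the planned ANOVA biased, or presenting adjustment as a remedy for the exclusions.

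**What to change.** Before outcome data are reviewed:

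- Add pre-operative glenoid version, inclination and depth of bone loss as prespecified covariates in the stated model, and keep the surgeon random effect. Do this for each deviation measure in Data Sheets (the three center-peg positions, version and inclination). State whether each is analyzed as signed or absolute, since one value of R² need not apply to all of them.
- For outcome three, name one continuous pre-operative severity measure, for example depth of bone loss, or measured minus estimated pre-morbid version. In a separate model that also contains surgeon, report the group-by-severity estimate with its 95% confidence interval, labelled exploratory. State that a null result does not show equal performance across severity.
- Leave surgeon-specific contrasts optional, and deal with the post-randomization exclusions as a separate matter.

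No new data are needed, but the investigators must choose the severity measure. The adjusted model spends 3 df and widens intervals by about 2% if the covariates explain nothing. The interaction spends a further 3 df with four groups, or 4 with five, in its own model.
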